- Safety population: all subjects who have received any amount of study drug. Subjects will be analyzed as treated.

Efficacy analyses

Descriptive summary statistics: Continuous variables will be summarized using descriptive statistics (n, mean, standard deviation, median, minimum, and maximum). Categorical variables will be summarized showing the number and percentage (n, %) of patients within each classification.

Safety analyses

Safety and tolerability will be assessed through documentation of TEAEs and vital signs and, as available, clinical laboratory and physical examination findings, and any other parameters relevant to safety.

Table 1: Schedule of Assessments

Assessment	Screening Day -7 to -1	Treatment		Post-Treatment Monitoring During Hospitalization ¹								Out-patient Follow Up ¹
		D1 (pre-dose) baseline	D1 (post-dose)	D2	D3	D4	D5	D6	D7	D10	D14/ Dis- charge ¹	
Informed consent	X											
Eligibility check	X											
Radiographic studies	X ²							X ⁴				
Electrocardiograms	X ³							X ⁴				
SARs-CoV-2 Testing ⁵	X							X ⁴				
Serology (HBsAg, anti-HCV, and anti-HIV 1/2 tests)	X ⁶											
Demographics, Medical History, COVID-19 Symptom History ⁷	X											
Pregnancy test ⁸	X											
Physical examination	X ⁹							X ⁴				
Vital signs	X	X ¹⁰	X ¹⁰						X ¹¹			
SpO ₂	X ¹²	X ¹³	X ¹³						X ¹¹			
Temperature	X	X ¹³	X ¹³						X ¹¹			
Randomization	X											
Height ¹⁴ and weight	X	X ¹⁵										
Study drug administration		X										
WHO Ordinal Scale score ¹⁶	X		X	X	X	X	X	X	X	X	X	X
Oxygen utilization ¹⁷	X	X	X						X ¹¹			
Safety laboratory testing (hematology, clinical chemistry), Urinalysis	X ¹⁸	X ¹⁸							X ¹¹			
Blood sampling (serum) for ATYR1923 PK ¹⁹			X					X		X	X	X
Blood sampling for Jo-1 Ab and ADA			X					X		X	X	X
Blood sampling for cytokines/chemokines			X	X				X		X		X
Blood sampling for cardiac troponins, D-dimers, ferritin, NT-proBNP			X	X	X			X		X		X
Tryptase			X ²⁰									

Assessment	Screening	Treatment		Post-Treatment Monitoring During Hospitalization ¹								Out-patient Follow Up ¹	
		Day -7 to -1	D1 (pre-dose) baseline	D1 (post-dose)	D2	D3	D4	D5	D6	D7	D10	D14/ Discharge ¹	
Adverse events ²¹				X	X	X	X	X	X	X	X	X	X
Concomitant medications	X ²²	X	X	X	X	X	X	X	X	X	X	X	X
Intensive care unit utilization / Ventilation status ²³										X			

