8.6.5. Safety Laboratory Tests

Blood and urine samples for clinical safety laboratory assessments will be collected at the time points designated in [Table 1](#) at Screening and Day 1. After Day 1, clinical safety laboratory assessments are to be collected per SOC. Note that if screening safety laboratory assessments are performed within 2 days of Day 1, then the pre-dose Day 1 safety laboratory assessments need not be repeated.

These samples will be analyzed at the local laboratory following their laboratory standard operating procedures (SOPs).

The following parameters may be collected and documented in the eCRF, as available per SOC:

- Clinical chemistry (serum quantitatively):
 - Total bilirubin, alkaline phosphatase, aspartate aminotransferase (AST), alanine aminotransferase (ALT), lactate dehydrogenase (LDH), creatine phosphokinase, albumin, creatinine, blood urea nitrogen, total protein, glucose, , sodium, potassium, calcium and chloride,.
- Hematology (blood quantitatively):
 - Leukocytes, erythrocytes, hemoglobin, hematocrit, thrombocytes, partial automated differentiation (lymphocytes, monocytes, eosinophils, basophils, neutrophils), mean corpuscular volume, mean corpuscular hemoglobin, mean corpuscular hemoglobin concentration
- Coagulation (blood quantitatively):
 - Prothrombin time (reported in seconds and as international normalized ratio) and partial thromboplastin time
- Urinalysis (semi-quantitative by dipstick):
 - Hemoglobin, urobilinogen, ketones, glucose, protein
 - Microscopy is to be performed if indicated by an abnormal and clinically significant result. Culture results, if conducted per SOC, are to be documented.

- Cardiac troponins, ferritin, B-type natriuretic peptide (BNP) or N-terminal-pro-BNP, and D-dimer.

In case of unexplained or unexpected clinical laboratory test values, the tests will be repeated as soon as possible and followed up until the results have returned to the normal range, baseline level and/or an adequate explanation for the abnormality is found. The clinical laboratory will clearly mark all laboratory test values that are outside the normal range and the Investigator will indicate which of these deviations are clinically significant. These clinically significant deviating laboratory results will then be recorded as AEs and the relationship to the treatment will be indicated (see also [Section 9.2](#)).

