10.1.2.3.2. Clinical Laboratory

Clinical laboratory data will be listed, and will also be flagged if the parameter is outside the reference range. A summary of all data outside the reference range of the clinical laboratory will be provided. Clinical laboratory data will be presented descriptively, where applicable.

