#### 3.4.3 Exploratory

- Change from baseline in supplemental oxygen requirement at Days 3, 5, 10, 14, and discharge.
- Proportion of patients requiring intubation, and among those patients, number of days in intubation.

- Change from baseline in inflammatory biomarkers and cytokines including: C-reactive protein (CRP), interferon gamma (INF  $\gamma$ ), interleukin (IL)-6, IL-2, IL-7, IL-10, tumor necrosis factor-alpha (TNF $\alpha$ ), macrophage inflammatory protein-1 (MIP1), C-X-C motif chemokine 10 (CXC-10), and monocyte chemoattractant protein-1 (MCP-1).
- Change from baseline in potential markers of COVID-19, including serum ferritin and D-dimer.

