#### 4.10.3 Clinical Laboratory Evaluation

Local laboratories will be used for laboratory safety evaluations in this study. [Table 6](#) shows the list of laboratory parameters. Laboratory results will be graded as low, normal, or high comparing to the normal range provided by the local laboratories .

All laboratory values will be reported in local units and in alphabetical order.

For by-visit summaries, the first non-missing assessment (including repeat assessments) recorded at each visit will be used. Optional laboratory parameters (Creatine Phosphokinase, Lactate Dehydrogenase (LDH)) will not be summarized by treatment group, only listed. Separate summaries for Hematology, Clinical Chemistry, Coagulation, Urinalysis and Serology (Baseline only) to be produced will be:

- for laboratory values reported as a character value, such as 'negative', number and percentage of subjects for each outcome by scheduled visit
- for continuous laboratory values, number and percentage of subjects with values outside normal range by scheduled visit,
- for continuous laboratory values, shifts from baseline in relation to normal range at all scheduled visits.

By-patient listings of all laboratory data, with abnormal values flagged, will be provided for Serology, Hematology, Clinical Chemistry, Coagulation and Urinalysis test results. Further marker of anaphylaxis: Tryptase will be listed by subject.

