#### 4.11.3 Biomarker

Continuous biomarker values and change from baseline will be summarized descriptively per assessment time point using only values from scheduled visits for Safety Analysis Set.

- inflammatory biomarkers and cytokines: C-reactive protein (CRP), interferon gamma (INF- $\gamma$ ), interleukin (IL)-6, IL-2, IL-7, IL-10, tumor necrosis factor-alpha (TNF $\alpha$ ), macrophage inflammatory protein-1 (MIP1), C-X-C motif chemokine 10 (CXC-10), and monocyte chemoattractant protein-1 (MCP-1), if available.
- potential markers of COVID-19 disease: Troponin I, Troponin T, NT-proBNP, BNP, Ferritin and D-dimer.

By-patient listings of all biomarker results including unscheduled assessments will be provided.

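### The SAP plans no out-of-range count or shift table by arm for troponin, BNP/NT-proBNP, ferritin or D-dimer, although the protocol lists them as safety laboratory tests and promises a summary of all out-of-range laboratory data

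*SAP*

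**What the plan says.** **Protocol.** The list in Section 8.6.5, Safety Laboratory Tests, ends with "Cardiac troponins, ferritin, B-type natriuretic peptide (BNP) or N-terminal-pro-BNP, and D-dimer". The list is introduced with "The following parameters may be collected and documented in the eCRF, as available per SOC", and the samples are analysed at local laboratories. The Schedule of Assessments (Table 1) also gives most of these markers a sampling row of their own: "Blood sampling for cardiac troponins, D-dimers, ferritin, NT-proBNP". For laboratory results in general, Section 10.1.2.3.2 states: "A summary of all data outside the reference range of the clinical laboratory will be provided".

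**SAP, laboratory section.** Section 4.10.3 grades results as low, normal or high against the local laboratory's range. It plans counts of patients outside the range and shifts from baseline, by scheduled visit, for a closed set of panels: "Separate summaries for Hematology, Clinical Chemistry, Coagulation, Urinalysis and Serology (Baseline only) to be produced". Listings with abnormal values flagged are planned for the same panels. Table 6, which names the parameters, has no troponin, BNP, NT-proBNP, ferritin or D-dimer.

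**SAP, biomarker section.** Section 4.11.3 handles the markers as "potential markers of COVID-19 disease: Troponin I, Troponin T, NT-proBNP, BNP, Ferritin and D-dimer". It summarises values and change from baseline descriptively, using scheduled visits only, and adds by-patient listings that include unscheduled results. The matching exploratory endpoint in Section 3.4.3 reads "Change from baseline in potential markers of COVID-19, including serum ferritin and D-dimer".

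**SAP, table of changes (Section 3.2).** The single entry concerns the time-to-improvement endpoint.

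**The concern.** Safety is the primary objective. For routine haematology and chemistry, the SAP gives the reader a count of patients outside the range, by arm, that does not depend on anyone's clinical judgement. For the cardiac markers it gives no such count. A raised troponin or BNP enters a patient count only if the investigator judges it clinically significant and reports an adverse event. There is then no independent laboratory tabulation against which to check that judgement, and the protocol's undertaking to summarise all out-of-range laboratory data is not met for these tests.

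Two features of SAP 4.11.3 add to the gap. Its summaries use scheduled visits only, so a marker measured between visits, possibly because something was suspected, is excluded from them. They also pool values from local laboratories at about 15 centres, where assays and units may differ.

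**Working it through.** The documents give no figure on this point, so there is none to reproduce. The check is a comparison of text, followed by a short calculation of what a count could show.

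**1. Are the markers safety laboratory tests?** Yes, by their place in Protocol 8.6.5. The same section has the laboratory mark every value outside the normal range.

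**2. Which outputs cover them?**

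| Output | Routine panels (SAP 4.10.3, Table 6) | Troponin I, Troponin T, BNP, NT-proBNP, ferritin, D-dimer (SAP 4.11.3) |
|---|---|---|
| Patients outside local range, by visit and arm | Planned, with some parameters listed only | Not planned |
| Shift from baseline against range | Planned, with some parameters listed only | Not planned |
| Values and change from baseline | Not among the 4.10.3 summaries | Mean, SD, median, minimum, maximum, n |
| By-patient listing | Abnormal values flagged | Unscheduled values included, no flag stated |
| Adverse event if clinically significant | Yes | Yes |

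All six analytes named in SAP 4.11.3 are missing from Table 6. Where Section 4.10.3 means to list a parameter without summarising it, as for creatine phosphokinase and LDH, it says so. It says nothing about the cardiac markers.

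**3. Is the departure disclosed?** No. The only entry in the table of changes concerns another endpoint.

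**4. Can the count be recovered from the planned statistics?** Not from the summaries. Mean, SD, median, minimum, maximum and n do not determine how many patients exceed a limit, still less when each local laboratory has its own limit. By-visit tables also do not show how many different patients were ever raised. The listing could be counted by hand, but the SAP does not say that it will carry reference ranges or flags.

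**5. Are pooled values safe to read?** SAP 4.2 calls for laboratory data in standard units, while SAP 4.10.3 calls for local units. Neither section deals with differences between assays. A count against each laboratory's own limit is less exposed to this problem.

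**6. What precision would a count have?** With 30 patients at 1:1:1, each arm has 30/3 = 10 and the two active arms together have 20. If every patient is tested (an assumption), exact (Clopper-Pearson) 95% intervals are:

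- 0/10: 0 to 30.8% (upper limit 1 − 0.025^(1/10) = 0.308)
- 1/10: 0.3 to 44.5%
- 3/10: 6.7 to 65.2%
- 0/20: 0 to 16.8% (upper limit 1 − 0.025^(1/20) = 0.168)
- 3/20: 3.2 to 37.9%

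The count would be descriptive and imprecise, as is every comparison in this unpowered study.

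**The case against.** Four things can be said for the plan.

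**The markers are more than averaged.** A reader might infer from SAP 4.11.3 that only means will be shown. That is wrong. SAP 4.2 adds SD, median, minimum, maximum and n, and every result is listed by patient. In many cases these would separate one large rise from several small ones. The claim that the planned output hides such differences altogether is not supported.

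**Raised values can be counted.** A reader might infer that cardiac injury is never counted by patient and arm. That too is wrong. Protocol 8.6.5 requires clinically significant deviations to be recorded as adverse events, and Protocol 9.1.1 treats laboratory changes needing therapy as adverse events. SAP 4.10.2 counts these by patient, system organ class, preferred term and severity. SAP 4.10.5 also summarises abnormal ECG findings. What remains is that the adverse event route rests on investigator judgement and coding, so it cannot serve as a check on that judgement.

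**The classification is defensible.** Protocol Table 1 separates these markers from the routine safety laboratory row, and the exploratory endpoint's list is open-ended. Protocol 10.1.2 leaves full analysis detail to the SAP. All this stands, but a marker can serve both purposes. Analysing it as a disease marker does not discharge the undertaking in Protocol 10.1.2.3.2, and the SAP does not say that the undertaking was narrowed.

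**Collection may be patchy.** Protocol 8.6.5 makes collection subject to standard of care, so denominators may be incomplete. That is a reason to report the number tested alongside the count, not to omit the count.

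**Conclusion.** The point holds in this form: no laboratory-based out-of-range count or shift table by arm is planned for troponin, BNP/NT-proBNP, ferritin or D-dimer, contrary to Protocol 10.1.2.3.2, and the SAP does not disclose the departure. Unscheduled values enter none of the marker summaries in SAP 4.11.3, and pooled scheduled values may mix assays and units.

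In size, this is a reporting gap of six analytes and two table types. It bears on the primary safety objective and is worth correcting, but it does not undermine the trial. The documents give no rate of cardiac marker elevation and no assay mix, so the number of patients whose elevation would go uncounted cannot be estimated.

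The conclusion assumes that the protocol's phrase about clinical laboratory data covers every test in Section 8.6.5. If it meant only the routine panels, the breach of the protocol falls away. The lack of a laboratory count for cardiac markers remains.

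**What to change.** 1. Add troponin I/T and BNP/NT-proBNP to SAP Table 6, with D-dimer and ferritin so that Protocol 10.1.2.3.2 is met. Apply the existing out-of-range and shift tables of SAP 4.10.3, graded against local reference ranges.
2. Those tables run by scheduled visit, so add two patient-level rows by arm: any troponin (I or T) newly above the local upper limit after dosing, and the same for BNP/NT-proBNP. Include unscheduled values. Show patients with no baseline result separately.
3. Use patients tested as the denominator and print that number. SAP 4.3.1 puts all patients of the analysis set in the denominator even when the outcome is missing, so state the exception explicitly.
4. Flag abnormal values in the SAP 4.11.3 listing, and keep that section's descriptive summaries.
5. Reconcile the unit statements in SAP 4.2 and 4.10.3.
6. Record the addition in the table of changes and label it post hoc. SAP version 3.0 is itself a post-unblinding revision, and Section 3.2 requires that label for analyses added after database lock.

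The cost is a few extra table rows from data already collected, provided that local ranges for these tests are on file. No sample is added, and neither sample size nor any test changes. The downside is that denominators may be incomplete and intervals wide. Version 2.0 of the SAP added urinalysis grading rules after unblinding, so a change of this kind has a precedent in the same document.

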**Table 6 List of Laboratory Parameters**

Hematology	RBC WBC Basophils (absolute and %) Eosinophils (absolute and %) Lymphocytes (absolute and %) Monocytes (absolute and %) Neutrophils (absolute and %) Platelets Hematocrit Hemoglobin Mean corpuscular volume (MCV) Mean corpuscular hemoglobin (MCH) Mean corpuscular hemoglobin concentration (MCHC)
Clinical Chemistry	Total bilirubin Alkaline phosphatase Aspartate aminotransferase (AST) Alanine aminotransferase (ALT) Lactate dehydrogenase (LDH) Creatine phosphokinase Albumin Creatinine BUN Total Protein Glucose Sodium Potassium Calcium Chloride
Coagulation	Prothrombin time (PT) activated Partial thromboplastin time (PTT) International normalized ratio (INR)
Urinalysis	Hemoglobin Urobilinogen Glucose Ketones Protein Leukocyte Esterase Microscopy results: Urine RBC, Urine Squamous cell, Urine WBC
Serology (Baseline only)	Hepatitis B Virus Core Antibody Hepatitis B surface antigen (HBsAg) HIV-1 Antibody

	HIV-2 Antibody Hepatitis C antibody Hepatitis C Virus RNA
Marker of anaphylaxis	Tryptase

#### 4.10.4 Vital Signs and Physical Findings

Vital Signs will be presented in standard units and in alphabetical order including weight, height, BMI, systolic and diastolic blood pressure, respiratory rate, heart rate and temperature. Absolute value, change and percent change from baseline will be summarized at each visit.

A by-patient listing of all vital signs data will be provided by treatment group.

Physical examination results will be listed only.

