hypersensitivity pneumonitis and *P. acnes*-induced sarcoidosis, ATYR1923 treatment led to the reduction of several pro-inflammatory cytokines, including IL-6, MCP-1 and IFN- γ (Berkart et al., 2019). The immunomodulatory activity of ATYR1923 is likely exerted through interaction with the cell-surface receptor NRP-2, which is present on multiple immune cell types and upregulated on alveolar macrophages and inflammatory monocytes in response to inflammatory conditions in the lung. A potential therapeutic effect of ATYR1923 was also investigated in a murine acute lung injury model that reproduces key features of human ARDS. Treatment with ATYR1923 at 3.0 and 10 mg/kg led to a dose-dependent reduction of total neutrophil and alveolar macrophage counts in the lung at 24h post insult.

Thus, a strong scientific rationale exists to investigate ATYR1923 as a treatment for severe respiratory complications related to COVID-19 infection. aTyr is conducting the current study to evaluate ATYR1923 1 mg/kg and 3 mg/kg in adults with severe respiratory complications related to SARS-CoV2 infection. Eligible patients will be adults aged 18 to 75 years, who present with SARS-CoV2-related severe pneumonia not requiring mechanical ventilation. The patient or designated legal representative is required to provide informed consent before the performance of any study-related procedures. The primary objective is determination of the safety of ATYR1923 in this patient population. The effects of ATYR1923 on efficacy outcomes, including oxygen saturation levels, fever and clinical status, is a secondary objective. The effect of ATYR1923 on other outcome measures in this patient population also will be explored.

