8.3.3. Pulse Oximetry

To assess eligibility, one measurement of SpO₂ without supplemental oxygen should be attempted. If not clinically feasible, obtain the measurement with supplemental oxygen. The corresponding level of supplemental O₂ use is to be recorded in the eCRF at screening to confirm eligibility.

On Day 1, SpO₂ readings will be recorded pre-dose then at 1 and 4 hours (\pm 15 minutes) after the start of infusion (SOI).

After Day 1, SpO₂ is to be measured per SOC and recorded in the eCRF, as per [Table 1](#).

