8.3.4. Vital Signs and Temperature

Vital signs include blood pressure, heart rate, and respiration rate, and temperature.

Day 1 vital signs are to be obtained pre-infusion and at 15 and 30 minutes (± 5 minutes) and at 1, 2, and 4 hours (± 15 minutes) after the start of infusion (SOI). Vital signs will include blood pressure (systolic and diastolic), heart rate, and respiratory rate, recorded after resting for 5 min.

After Day 1, temperature and vital signs are to be measured per SOC and recorded in the eCRF, as per [Table 1](#).

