#### **Analysis Visit Window:**

By visit summaries will be based on the nominal/scheduled visit as reported in eCRF and will be grouped by Day 1, 2, 3, 4, 5, 6, 7, 10, 14, 28 and 60.

For (telephone contact) TC follow up visits and unscheduled Discharge visits, analysis visit windows will be applied as in [Table 2](#) and [Table 3](#) below. Note, analysis visit windows are only used for by visit summaries, not for time to event calculation which will be based on actual date of data collected. TC follow up visits and Discharge visits that are not in any of the analysis visit windows, will be excluded from summaries and only presented in listings.

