**Table 3 Analysis Visit Window for unscheduled Discharge visits**

mapped to	Visit Window
Day 7	Day 8
Day 10	Day 10 ± 1 days
Day 14	Day 14 ± 2 days
Day 28	Day 28 ± 5 days
Day 60	Day 60 ± 5 days

In case several outcomes are available for the nominal/scheduled analysis visits, the latest non-missing result will be used for summaries.

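### On a literal reading, the SAP's Day 1 vital-sign tables keep only the latest value, so a transient change between 15 minutes and 2 hours appears in no by-arm vital-sign summary, and post-dose SpO2 is in no named summary or listing

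*SAP*

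**What the plan says.** **Collection.** Protocol 8.3.4 states "Day 1 vital signs are to be obtained pre-infusion and at 15 and 30 minutes" "and at 1, 2, and 4 hours", counted from the start of infusion. The signs taken at those times are specified by "Vital signs will include blood pressure (systolic and diastolic), heart rate, and respiratory rate, recorded after resting for 5 min". For SpO2, Protocol 8.3.3 says Day 1 "readings will be recorded pre-dose then at 1 and 4 hours"; Table 1, footnote 13 puts temperature on the same times.

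**Analysis.** SAP 4.10.4 lists weight, height, BMI, blood pressure, respiratory rate, heart rate and temperature. Its instruction is "Absolute value, change and percent change from baseline will be summarized at each visit". It names no Day 1 time points, worst value or abnormality threshold. It also provides a by-patient listing of all vital signs.

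SAP 4.2 defines the visit: "By visit summaries will be based on the nominal/scheduled visit as reported in eCRF and will be grouped by Day 1, 2, 3, 4, 5" and onward to Day 60. Where a visit has several outcomes, "the latest non-missing result will be used for summaries".

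**SpO2.** It is not among the parameters of SAP 4.10.4. The SAP's only named use of it is a baseline category in SAP 4.7 (at or below 86%).

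**The concern.** Safety is the primary objective, and Protocol 10.1.2.3 includes vital signs among the means of assessing it. Protocol 9.9 says that infusion reactions arise close in time to the infusion and names hypotension, dyspnea and hypoxia as cardiorespiratory risks. The possible earlier reactions described in Protocol 2.1.1 were mild and transient. The most informative readings for such an effect are therefore the early ones, and a single Day 1 row holding the 4 h value leaves them out.

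At stake is the comparison with placebo. In severe pneumonia, a fall in saturation or a rise in respiratory rate is easily put down to the disease, so whether an investigator reports it as an adverse event is a matter of judgement. A by-arm summary of the measured values does not depend on that judgement. The schedule collects what such a summary needs, but the SAP text does not ask for it.

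**Working it through.** The plan states no figure on this point, and SAP 3.1.4 reports no power calculation, so there is nothing to reproduce. The check is a count of scheduled readings under the SAP's rule.

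**Inputs**
- Patients: N = 30, randomised 1:1:1, so 10 per arm (SAP 3.1.4).
- Times after the start of infusion for blood pressure, heart rate and respiratory rate: k = 5 (Protocol 8.3.4).
- Times after dosing for temperature: k = 2 (Protocol Table 1, footnote 13).
- Times after dosing for SpO2: k = 2 (Protocol 8.3.3).
- Values kept per patient for Day 1: 1 for each parameter in SAP 4.10.4 (latest-value rule, SAP 4.2) and 0 for SpO2.
- Assumption: all 30 patients are dosed and have every reading.

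**Formula.** Scheduled = N × k; summarised = N × (values kept); outside the summary = the difference.

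| Parameter | Scheduled | Summarised | Outside the by-arm summary |
|---|---|---|---|
| Blood pressure, heart rate, respiratory rate (each) | 30 × 5 = 150 | 30 × 1 = 30 | 120 (120/150 = 80%) |
| Temperature | 30 × 2 = 60 | 30 × 1 = 30 | 30 (30/60 = 50%) |
| SpO2 | 30 × 2 = 60 | 30 × 0 = 0 | 60 (all) |

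Per arm, for each of the first three parameters: 10 × 5 = 50 scheduled, 10 summarised, 40 not. The percentages do not depend on N.

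**What the Day 1 row would show.** The mean changes in systolic pressure below (mm Hg, at 15 min, 30 min, 1 h, 2 h and 4 h) are assumed for illustration only.
- −5, −20, −20, −10, 0: the row shows 0; the lowest value is −20.
- −5, −20, −15, −10, −5: the row shows −5; the lowest value is −20.
- −20 throughout: the row shows −20.

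The rule hides a transient change and preserves a sustained one.

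**Does the general rule govern vital signs?** The SAP sets a different rule where its authors wanted one. SAP 4.10.3 takes the first available laboratory value at each visit, and SAP 4.11.3 summarises biomarkers by assessment time point. SAP 4.10.4 does neither, so the default in SAP 4.2 applies as written.

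**The case against.** **The early readings are not lost.** A reader might infer that infusion-period changes disappear from the safety output altogether, or that 80% of the readings go unused. The documents do not support that. SAP 4.10.4 lists all vital signs by patient, and about 10 patients per arm can be inspected individually. Protocol 8.6.3 has clinically significant changes in vital signs or pulse oximetry after dosing recorded as adverse events, and SAP 4.10.2 and 4.10.2.1 tabulate those, including suspected infusion reactions. This stands and narrows the point to the by-arm vital-sign summaries.

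It does not remove the point. A listing makes no comparison between arms, and the adverse event route depends on the investigator's judgement. Protocol 8.6.3 and 9.2 also have events within 24 hours recorded as separate signs and symptoms and not as an infusion-reaction diagnosis, while the SAP does not say how suspected reactions are then identified.

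**The rule may not be meant for planned time points.** The latest-value sentence follows the tables that map telephone and discharge visits, and it can be read as settling duplicate records. The table shells and eCRF are not supplied, and shells could display planned times. This stands as a limit on certainty: the finding is about the SAP text. If the shells do show time points, the SAP should say so.

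**SpO2 is not a dropped endpoint.** A reader might infer otherwise from the sentence in Protocol 2.2, "The effects of ATYR1923 on efficacy outcomes, including oxygen saturation levels, fever and clinical status, is a secondary objective". But Protocol 3.2 and SAP 3.4.2 list no SpO2 endpoint, and the protocol schedules SpO2 separately from vital signs. Oxygenation is analysed through oxygen duration, oxygen requirement and the WHO scale, and a spot SpO2 is hard to interpret without the oxygen level. All of that stands. It still leaves a scheduled Day 1 measurement without a named display, and because SpO2 is separate from vital signs, the vital-sign listing does not clearly cover it.

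**Purpose and timing.** Protocol 8.3.4 does not say that its schedule exists to detect infusion reactions; that link is an inference from Protocol 9.9. The times run from the start of infusion, so some readings may fall during it.

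**Conclusion.** The point holds for the summary tables and should be corrected. Read literally, SAP 4.2 and 4.10.4 leave 80% of the readings after the start of infusion for each of blood pressure, heart rate and respiratory rate, and half of the post-dose temperature readings, outside the by-arm summaries. A change between 15 min and 2 h that has resolved by 4 h would appear in no by-arm vital-sign summary. No post-dose SpO2 reading has a named summary or listing.

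The counts assume 30 dosed patients with complete data. They also assume that the latest Day 1 value is the 4 h one; an unscheduled later reading, or a missing 4 h reading, would change which value is kept but not that only one is. The primary endpoint, incidence of treatment-emergent adverse events, is unaffected. What is lost is a by-arm view of early measured changes in a trial whose primary question is safety.

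**What to change.** In SAP 4.10.4:
- Summarise Day 1 blood pressure, heart rate and respiratory rate at pre-infusion, 15 min, 30 min, 1 h, 2 h and 4 h, and temperature at pre-dose, 1 h and 4 h, as values and changes from baseline by arm.
- State that Day 1 is exempt from the latest-value rule in SAP 4.2.
- Add Day 1 SpO2 (pre-dose, 1 h, 4 h) to both the summaries and the by-patient listing.
- Optionally, add a descriptive worst value within 4 h by arm.

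SAP version 3.0 already follows unblinding, so label the added displays post hoc where SAP 3.2 requires it. The cost is SAP wording and one or two extra descriptive tables; no new data collection is needed.
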